### **4.4 Withdrawal and discontinuation**

Participants will discontinue from the study in case of withdrawal of their informed consent or premature participant withdrawal (i.e. before Lab visit 3). In this case, the collected study-related

data and blood samples will be destroyed. After data analysis, study-related data will be anonymized, except when the concerned participant will expressly renounce to this right.

## 5 STATISTICS AND METHODOLOGY

### 5.1. Statistical analysis plan and sample size calculation

Our null hypothesis posits that the consumption of our plant-based, food-grade beverage does not result in a statistically significant difference in blood leucine levels compared to the consumption of an animal-based drink currently available in the market (Resource, Nestlé). Specifically, we anticipate that the leucine level attained by our plant-based drink does not exceed 90% of the level achieved by the animal-based alternative.

The study employs a crossover randomized controlled trial (RCT) design to investigate differences in leucine absorption, as measured by Area Under the Curve (AUC), following the consumption of animal drink A, animal drink B, and plant drink C. Each participant serves as their own control, receiving each of the three treatments in a randomized sequence over separate periods.

Detailed statistical plan:

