### 3 STUDY OBJECTIVES AND DESIGN

#### 3.1 Hypothesis and primary objective

##### Hypothesis:

We hypothesize that our plant-based, food-grade drink will result in blood leucine levels reaching up to 90% of those achieved by consuming an existing animal-based drink (Fresubin by Fresenius Kabi) or a comparable self-formulated animal-based drink. The self-formulated drink will contain the same ingredients as the plant-based one, except that the plant-based proteins will be replaced with animal-based whey protein. Primary objective: The objective of the study is to quantitatively assess the bioavailability of leucine in the blood following the consumption of a novel, but fully food-grade plant-based protein drink. This assessment will be compared to the bioavailability observed after consuming a animal-based protein drinks (commercial and self-formulated). By measuring leucine levels in the blood using High-Performance Liquid Chromatography (HPLC), the study aims to determine whether the plant-based drink can match or exceed the bioavailability of amino acids typically seen in animal protein sources, thereby offering a viable nutritional alternative for those seeking plant-based diets.

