#### 3.2 Primary endpoint

Primary endpoint: Leucine bioavailability in blood (HPLC), assessed by Area Under the Curve (AUC). We specifically chose leucine as this is the primary amino acids that triggers the synthesis of new proteins in the muscle via mechanistic target of rapamycin ([name] et al., 2020). Typically, when a protein source is rich in leucine and consumption of it leads to a high level of leucine in the blood after consumption, like with whey protein, it promotes more muscle protein synthesis compared to a drink based on a single plant protein source, such as soy. Therefore, with our new

drink, we aim to optimize the appearance of leucine in the blood, which is a good indicator of protein synthesis in resting muscles. Age does affect bioavailability and protein synthesis (Schiaffino et al., 2013), hence, for this pilot trial we opt to study young, healthy individuals, males and females.

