### 3.4. Study intervention

Participants will be administered three different drinks in a randomized crossover order. These drinks are:

- Animal-based A: A commercially available high protein drink, based on animal proteins (Fresubin Protein Energy Fresenius Kabi).
- Animal-based B: A homemade drink containing animal-based proteins, using a specific animal-based protein isolate mix.
- Plant-based A: A homemade drink containing plant-based proteins, formulated to have the same macronutrient content as the animal-based drinks.

\*\* all drinks will have the same total protein content, and all participants will receive the same total amount of proteins.

Composition of drinks:

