Participants will arrive fasted at the lab. After a 60 min seated rest, a baseline blood sample will be taken 30 minutes prior to consuming the drink. After consuming the assigned drink, a second, third and fourth blood sample will be collected 30, 60 and 90 minutes later, to determine leucine appearance (Area Under the Curve, AUC). This procedure will be repeated three times, each with a different drink, with 5-7 days washout in between. The primary measure of the study is the leucine content in the blood, determined using High-Performance Liquid Chromatography (HPLC), to assess the bioavailability of the proteins in the drinks.

We are testing two kinds of animal-based protein drinks and one plant-based protein drink. The reason for this is we are creating alternatives to the nutritional drinks currently sold by companies like Nestlé and Fresubin (FSMP products). We have made a drink using whey (which comes from animals) and another using a combination of pea and rice (which are plants), ensuring both have the same mix of nutrients as the ones you can buy now. We want to see if our drinks are better at delivering leucine to the body compared to the existing products.

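### Sections 3.1 and 5.1 state the plant-versus-animal question inconsistently, and section 5.1 plans no plant/animal ratio and promises pairwise intervals only after a significant ANOVA

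*Combined protocol and SAP*

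**What the plan says.** Section 3.1 hypothesises that the plant beverage "will result in blood leucine levels reaching up to 90% of those achieved by consuming an existing animal-based drink (Fresubin by Fresenius Kabi"); the sponsor's own whey drink is given as an alternative reference. The primary objective in the same section then says "the study aims to determine whether the plant-based drink can match or exceed the bioavailability of amino acids" seen with animal protein.

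Section 5.1 states as its null that the plant drink "does not result in a statistically significant difference in blood leucine levels compared to the consumption of an animal-based drink". It describes this comparator as "currently available in the market (Resource, Nestlé"). The next sentence, offered as a specification of that null, reads "we anticipate that the leucine level attained by our plant-based drink does not exceed 90% of the level achieved by the animal-based alternative". In section 3.4 the marketed drink is a different product: "A commercially available high protein drink, based on animal proteins (Fresubin Protein Energy Fresenius Kabi"). The synopsis and sections 3.1 and 4.3 also give Fresubin.

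The endpoint in section 3.2 is "Leucine bioavailability in blood (HPLC), assessed by Area Under the Curve (AUC"), without saying whether the AUC is total or incremental. The analysis in 5.1 is a normality test, an ANOVA reported by its overall F and p-value (item 2), and post-hoc comparisons with adjusted p-values and confidence intervals if the ANOVA is significant (item 3). Item 4 adds effect sizes of the variance-explained kind. These do not depend on the ANOVA result, but they are not plant/animal ratios.

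**The concern.** A reader cannot tell which result would support the hypothesis. Under the 90% wording, 90% could be a ceiling, a target or part of the null. Under the objective, the benchmark is 100% or more. An observed ratio of 0.85 or 0.95 could be called success or failure.

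The analysis does not settle this. A test of zero difference can show that the drinks differ, in either direction. It cannot show that they match or that the plant drink stands at 90%. With the null worded as it is, a non-significant F invites a conclusion of no difference that the data would not support.

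Section 2 says the pilot will be used to choose drinks and set the size of a larger trial. Both decisions need the estimated ratio and its precision, whether or not the F is significant.

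**Working it through.** **The plan's own figure.** The code in 5.1 gives d = 8,000/6,100 = 1.311 and f = √(d²/(1+d²)) = 0.795. The solver returns 18.59, and dividing by 1 + 2 × 0.5 = 2 gives 9.29, which agrees with the stated 9-10. Whether that adjustment is sound is a separate question, and nothing below uses it. What matters here is the target: 20,000 against 28,000, a ratio of 0.714, and not 0.90 or 1.00.

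**How often would the pairwise intervals be promised?** Inputs from 5.1: animal mean 28,000, SD 6,100 (animal) and 2,000 (plant), r = 0.5, alpha 0.05, n = 12. Assumptions: the two animal drinks have equal means, and the leucine level in the hypothesis is the AUC.

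With a common SD, the repeated-measures F has noncentrality λ = n·Σ(μᵢ − μ̄)² / (SD²(1 − r)) on 2 and 2(n − 1) degrees of freedom.

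At a ratio of 0.90 the means are 28,000, 28,000 and 25,200, and Σ(μᵢ − μ̄)² = (2/3) × 2,800² = 5,226,667. At n = 12, λ = 12 × 5,226,667 / (6,100² × 0.5) = 3.37. The critical F(2, 22) is 3.44 and the F is significant in 31.6% of trials.

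| True ratio | λ (n = 12, r = 0.5) | F significant |
|---|---|---|
| 0.90 | 3.37 | 32% |
| 0.80 | 13.48 | 88% |
| 0.714 | 27.52 | 99.5% |
| 1.00 | 0 | 5% |

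Sensitivity at a ratio of 0.90 (the plant-SD and log-scale rows are simulated):

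| Model | n = 12, r = 0.3 | n = 12, r = 0.5 | n = 12, r = 0.8 | n = 14, r = 0.5 |
|---|---|---|---|---|
| Common SD 6,100 | 24% | 32% | 68% | 37% |
| Plant SD 2,000 | about 29% | 37% | 54% | 43% |
| Log AUC, CVs 10% and 21.8% | 33% | 42% | 67% | about 50% |

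The n = 14 column is included because the synopsis and section 4.3 aim to enrol 14, while 4.1 and 5.1 say 12. The range of r is assumed; the documents give only 0.5.

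**What precision would a ratio have?** For a paired log ratio, the log-SDs are √ln(1 + 0.10²) = 0.0998 (plant, 2,000/20,000) and √ln(1 + 0.218²) = 0.2153 (animal, 6,100/28,000). With r = 0.5, the SD of the log ratio is √(0.0998² + 0.2153² − 0.0998 × 0.2153) = 0.187. The 95% CI factor at n = 12 is exp(2.201 × 0.187/√12) = 1.126. If the plant drink had the animal CV, the SD would be 0.215 and the factor 1.147. At an observed ratio of 0.90, the smaller factor gives 0.80 to 1.01.

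**The case against.** **The wording.** A reader might count four conflicting framings, adding the closing paragraph of section 3.4: "We want to see if our drinks are better at delivering leucine to the body compared to the existing products". The documents do not support that count. The two 90% statements can be read as the same expectation of at most 90%. The sentence in 3.4 is motivation, and it covers both home-made drinks, one of which is whey. What stands is the conflict between at most 90%, matching or surpassing, and a no-difference null to which the 90% is attached.

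**The size.** A reader might infer that the F is non-significant in most trials at 90%. That holds at r = 0.5 with 12 participants, but not across the range: at r = 0.8 the F is significant in 54-68% of trials, and on the log scale at n = 14 and r = 0.5 it is about even. It is also significant more often if the animal drinks differ. With plant at 0.90 of Animal A and A at 0.90 of Animal B, λ = 9.14 and the figure is 72% at n = 12.

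**Where the harm falls.** The planning ratio is 0.714, and section 3.4 lists leucine at 0.8 against 1 g per 100 ml for the plant drink and Animal B. Near those ratios the condition on the ANOVA costs little. This limits the harm but does not remove it, because 90% is the stated hypothesis.

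**Omission, not prohibition.** Item 3 does not bar descriptive ratios or intervals, so the ratio remains recoverable. That is true, but choosing the estimator, scale and AUC definition after seeing the data is what a plan should prevent.

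**A formal 90% test.** A reader might infer that the trial should be sized for non-inferiority at 90%. The documents set no such margin, and an exploratory pilot does not need one.

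**Conclusion.** The point holds and should be fixed before analysis. The hypothesis, the objective and the null do not agree; the comparator in 5.1 is not a study drink; and the planned tests cannot show matching or a 90% level. At the hypothesised ratio of 0.90, the interval the pilot needs is often not promised: the F is significant in about 32-42% of trials at n = 12, about 37-50% at n = 14, and 24-68% at n = 12 for r between 0.3 and 0.8. If all three drinks are equal it is significant in about 5%.

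These figures assume equal animal drinks, an animal SD of 6,100 and, where not varied, r = 0.5. The consequence is limited by the exploratory purpose and by the high chance of a significant F at ratios of 0.80 or below. The undefined AUC adds to the problem, because a fasting level shared by all drinks draws a total-AUC ratio towards 1. The documents give no fasting figure, so the effect cannot be sized.

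**What to change.** 1. In 3.1 and 5.1, use one statement of the hypothesis as a plant/animal AUC ratio, and say which side of 90% supports it.
2. Reconcile the comparator named in 5.1 with the drinks listed in 3.4.
3. In 5.1 item 3, report the within-participant plant/animal AUC ratio with a 95% CI for each animal drink, whatever the F shows. Fix the AUC definition, scale and estimator beforehand: for example, the geometric mean ratio from paired log AUC if total AUC is used, or a ratio of means with a Fieller-type interval if incremental AUC is used, since incremental values can be zero or negative.
4. State that a non-significant F is not evidence of matching, and that the ratio's CI is what is read against 90%. If an expected precision is quoted (a factor of about 1.13-1.15 either way at n = 12), label it as assuming a paired log ratio, the CVs from the cited study and r = 0.5.

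The cost is wording in 3.1 and 5.1, with the AUC definition also entered in 3.2. No new data, visits or participants are needed. The authors must commit to one meaning of 90% and one AUC definition, and must show that the precision is limited.

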#### 1. Test for Normality

The Shapiro-Wilk test, with a significance level ( $\alpha$ ) set at 0.05, will assess the normality of the distribution of our variables. This test helps determine the appropriateness of parametric tests such as ANOVA for our data.

#### 2. ANOVA

Our analysis will feature an ANOVA to examine the main effects of each drink (factors A, B, and C) and their interaction effects. This involves calculating sums of squares, degrees of freedom, mean squares, and F-statistics to understand each factor's impact and the interactions among them. We will interpret these effects, reporting the overall F-statistic and its associated p-value, and use a significance level to declare statistical significance.

#### 3. Post-hoc Comparisons

Should the ANOVA indicate significant effects, post-hoc comparisons using methods such as Tukey's HSD or Bonferroni correction will pinpoint specific group differences. We will report adjusted p-values and confidence intervals for each comparison, providing detailed insight into the drinks' effects.

# Updated standard deviation for the animal-based group
sd_animal_updated = 6100

# Given mean difference between plant and animal drinks
mean_diff = 8000

# Recalculate the effect size with the updated standard deviation
effect_size_updated = mean_diff / sd_animal_updated

# Calculate Cohen's f squared from the updated effect size (for ANOVA)
cohens_f_squared_updated = effect_size_updated**2 / (1 + effect_size_updated**2)
cohens_f_updated = sqrt(cohens_f_squared_updated)

# Setup for ANOVA power analysis
power_analysis = FTestAnovaPower()

# Number of groups (treatments)
num_groups = 3

# Desired power and alpha level
power = 0.8
alpha = 0.05

# Calculate required sample size per group with the updated effect size
sample_size_per_group_updated = power_analysis.solve_power(effect_size=cohens_f_updated,
                                                             alpha=alpha,
                                                             power=power,
                                                             k_groups=num_groups)

# Assumption for typical within-subject correlation in crossover dietary intervention studies
within_subject_correlation = 0.5

# Adjusting the sample size estimate for the crossover design
n_parallel = sample_size_per_group_updated
k = 3
r = within_subject_correlation

# Adjusted sample size for crossover design
n_crossover = n_parallel / (1 + (k - 1) * r)
```

```
print("Adjusted sample size for crossover design: {n_crossover}")
```

## 5.2. Handling of missing data and drop-outs

Missing data will be handled by complete case analysis. If the participant withdraws prematurely or drops out (i.e. before Lab visit 3), they will be replaced by recruitment of new subjects to ensure an adequate number of participants in the study.

# 6 REGULATORY ASPECTS AND SAFETY

## 6.1 Local regulations / Declaration of Helsinki

This study is conducted in compliance with the protocol, the current version of the Declaration of Helsinki, the ICH-GCP, the HRA as well as other locally relevant legal and regulatory requirements.

## 6.2 (Serious) Adverse Events and notification of safety and protective measures

An Adverse Event (AE) is any untoward medical occurrence in a patient or a clinical investigation subject which does not necessarily have a causal relationship with the trial procedure. An AE can therefore be any unfavourable or unintended finding, symptom, or disease temporally associated with a trial procedure, whether or not related to it.

A Serious Adverse Event (SAE) (ClinO, Art. 63) is any untoward medical occurrence that

- Results in death or is life-threatening,
- Requires in-patient hospitalisation or prolongation of existing hospitalisation,
- Results in persistent or significant disability or incapacity, or
- Causes a congenital anomaly or birth defect

Both Investigator and Sponsor-Investigator make a causality assessment of the event to the trial intervention, (see table below based on the terms given in ICH E2A guidelines). Any event assessed as possibly, probably or definitely related is classified as related to the trial intervention.

Relationship	Description
Definitely	Temporal relationship Improvement after dechallenge* Recurrence after rechallenge (or other proof of drug cause)
Probably	Temporal relationship Improvement after dechallenge No other cause evident
Possibly	Temporal relationship Other cause possible
Unlikely	Any assessable reaction that does not fulfil the above conditions
Not related	Causal relationship can be ruled out

\*Improvement after dechallenge only taken into consideration, if applicable to reaction

Both Investigator and Sponsor-Investigator make a severity assessment of the event as mild, moderate or severe. Mild means the complication is tolerable, moderate means it interferes with daily activities and severe means it renders daily activities impossible.

#### **Reporting of SAEs (see ClinO, Art. 63)**

All SAEs are documented and reported immediately (within a maximum of 24 hours) to the Sponsor-Investigator of the study.

If it cannot be excluded that the SAE occurring in Switzerland is attributable to the intervention under investigation, the Investigator reports it to the Ethics Committee via BASEC within 15 days.

#### **Follow up of (Serious) Adverse Events**

Describe the follow up procedures of participants terminating the study with reported ongoing (S)AEs until resolution or stabilisation.

#### **Notification of safety and protective measures (see ClinO, Art 62, b)**

If immediate safety and protective measures have to be taken during the conduct of the study, the investigator notifies the Ethics committee of these measures, and of the circumstances necessitating them, within 7 days.

#### **6.3 (Periodic) safety reporting**

An annual safety report (ASR) is submitted once a year to the local Ethics Committee by the Investigator (ClinO, Art. 43 Abs 1).

#### **6.4 Amendments**

Substantial changes to the study setup and study organization, the protocol and relevant study documents are submitted to the Ethics Committee for approval before implementation. Under emergency circumstances, deviations from the protocol to protect the rights, safety and well-being of human subjects may proceed without prior approval of the Ethics Committee. Such deviations shall be documented and reported to the Ethics Committee as soon as possible. Substantial amendments are changes that affect the safety, health, rights and obligations of participants, changes in the protocol that affect study objective(s) or central research topic, changes of study site(s) or of study leader and sponsor (ClinO, Art. 29). A list of substantial changes is also available on [www.swissethics.ch](http://www.swissethics.ch). A list of all non-substantial amendments will be submitted once a year to the competent EC together with the ASR.

#### **6.5 Notification and reporting upon completion, discontinuation or interruption of the study**

Upon regular study completion, the Ethics Committee is notified via BASEC within 90 days (ClinO, Art. 38). The Sponsor-Investigator may terminate the study prematurely according to certain circumstances, e.g.

- Ethical concerns,
- Insufficient participant recruitment,
- When the safety of the participants is doubtful or at risk (e.g. when the benefit-risk assessment is no longer positive),
- Early evidence of harm or benefit of the experimental intervention

Upon premature study termination or study interruption, the Ethics Committee is notified via BASEC within 15 days (ClinO, Art. 38).

Template concerning the notification of completion, discontinuation or interruption of the clinical trial for this is available on [www.swissethics.ch](http://www.swissethics.ch).

All biological materials and health-related data are archived and encrypted in a coded format upon termination of data analysis for 10 years.

A final report is submitted to the Ethics Committee via BASEC within a year after completion or discontinuation of the study, unless a longer period is specified in the protocol (ClinO, Art. 38).

## 6.6 Insurance

In the event of study-related damage or injuries, the liability of the institution ETH Zürich provides compensation, except for claims that arise from misconduct or gross negligence.

# 7 FURTHER ASPECTS

## 7.1 Overall ethical considerations

The scientific value of this study lies in its evaluation of the bioavailability of leucine from a plant-based protein drink as compared to an animal-based one. This research is particularly relevant in the field of nutrition science, as it addresses the challenge of developing sustainable, plant-based protein sources that are nutritionally comparable to animal proteins. The study contributes significantly to the understanding of how plant-based diets can be optimized for enhanced human health, aligning with sustainability objectives in food production.

Our team has formulated a plant-based drink that, based on preliminary data and specific formulations using a variety of plant sources, is expected to increase the bioavailability of leucine compared to drinks made from a single plant protein source. This aspect is crucial as it opens the possibility of creating plant-based protein options that are not only environmentally sustainable but also nutritionally effective.

Currently, there is a gap in knowledge regarding how a beverage specifically optimized for amino acid bioavailability, particularly leucine, stacks up against traditional animal-based protein drinks. This study aims to fill that gap, providing valuable insights into the potential of plant-based proteins in meeting nutritional needs.

**Justification of Methodology:** High-Performance Liquid Chromatography (HPLC) has been selected for its accuracy in measuring specific amino acids, such as leucine, in blood samples. This method is known for its precision, making it ideal for quantifying amino acid levels accurately. The use of a randomized crossover design in this study ensures that each participant serves as their own control. This approach significantly enhances the reliability of the results, as it reduces the variability that can arise from individual differences between participants. Standard procedures like fasting and routine blood sampling are incorporated to accurately assess the bioavailability of nutrients. Fasting ensures that the baseline levels of amino acids are consistent across participants, while routine blood sampling allows for the tracking of changes in leucine levels over time following the consumption of the test drinks.

The balance of risk and benefits for the participants, and by extension, for society, is carefully considered in this study. Participation is voluntary, and participants are expected to visit the lab three times over a short period of three weeks, each visit lasting approximately 4 hours. They will be compensated CHF 100 for their time and expenses. The study involves minimal invasive procedures, including the consumption of an animal- or plant-based drink and blood sampling. Considering these aspects, the study is structured to maintain a fair balance between risks and

benefits, ensuring ethical integrity and participant safety while aiming to contribute valuable insights to the field of nutrition science.

